Protocol CMUH110-REC2-070

The Effect of Lactobacillus Delbrueckii Subsp. Bulgaricus on Human's Weight Reduction

Document type: Study Protocol with Statistical Analysis Plan (SAP)

Version number 02

Document status: Final report

Release date 03-Feb-2023

Author: [REDACTED]

Number of pages: 28

IRB/REC No. :	CMUH110-REC2 -070
Page No. :	2/28

Table of contents

Table of contents2

Background3

Methods and Design.....4

Results7

Appendix14

IRB/REC No. :	CMUH110-REC2-070
Page No. :	3/28

Background

In recent years, probiotic supplements have become increasingly popular in daily life for preventing diarrhea, easing vaginal and urinary infections, or preventing autoimmune diseases [1–3]. Probiotics cause the formation of a properly balanced gut bacterial population, with balance between pathogens and the bacteria necessary for normal functioning of the organism, and may improve immune system function and nutrient absorption. Recently, the gut microbiota was found to be involved in various metabolic pathways and energy balance regulation [4, 5]. The composition of the gut microbiota differs between obese and normal weight individuals [6, 7]. Dietary alteration of the gut microbiome is a target for treating obesity [8]. However, clinical trials examining the influence of probiotics on obesity-related factors have yielded inconsistent outcomes. Some studies have demonstrated weight loss in participants supplemented with *Lactobacilli* and *Bifidobacteria*, even while maintaining their normal diet and lifestyle over the study's duration [9,10]. In a 12-week trial, participants consuming *L. gasseri* experienced significant reductions in visceral fat, body mass index, waist and hip circumference, and body fat mass compared to the control group [11]. Conversely, another trial involving *L. rhamnosus* supplementation alongside an energy-restricted diet did not significantly impact weight loss in all participants but showed a reduction in weight in females [12]. Systematic review, encompassing 19 randomized trials with 1,412 participants, revealed diverse outcomes [13]. Some studies report significant decreases in body weight and/or body fat with probiotics, while others indicate no effect or even increased body weight. It suggests that specific probiotics have the potential to serve as health supplements for treating or preventing obesity and overweight.

Lactobacillus is a type of lactic acid bacterium commonly found in the human gastrointestinal tract and in fermented dairy products such as cheese, yogurt, and kefir [14]. The isolation of specific probiotic strains for targeted application is a strategy for improving the efficacy of probiotic supplements. Some species of *Lactobacillus*, such as *L. gasseri* and *L. rhamnosus*, have been evaluated for inducing weight loss [15]. *Lactobacillus delbrueckii* ssp. *bulgaricus* (*L. bulgaricus*) is one of the most common lactobacilli starters used in the manufacture of a large variety of fermented milk products. *L. bulgaricus* is reported to exhibit an outstanding inhibitory effect on pancreatic lipase activity in vitro and effectively managed the fat and weight accumulation and reversed the increased blood lipid, sugar, and insulin levels caused by a high-fat diet in mice [16]. Our hypothesis posits that *L. bulgaricus* can contribute to the reduction of body weight and alleviate health risk factors associated with obesity in overweight individuals. Thus, the objective of this study was to examine the effectiveness of daily *L. bulgaricus* supplementation in weight management among overweight participants. The primary goal is to evaluate its impact on lowering body weight and addressing health risk factors related to obesity, including blood lipid levels, sugar regulation, and insulin levels.

IRB/REC No. :	CMUH110-REC2-070
Page No. :	4/28

Methods and Design

Participants:

The participants were recruited from the patients of Endocrinology and Metabolism Department at China Medical University Hospital, followed by the verification of inclusion and exclusion criteria through interviews. The inclusion criteria comprised: (1) age ≥ 20 years old; (2) overweight (BMI ≥ 23) or body fat percentage $\geq 25\%$ for males and $\geq 30\%$ for females; (3) having any of the following risk factors: atherosclerotic cardiovascular disease (ASCVD), type 2 diabetes, age ≥ 45 years for males, ≥ 55 years for females or postmenopausal, hypertension, dyslipidemia (total cholesterol(CHOL) > 200 mg/dL or low-density lipoprotein cholesterol (LDL-C) > 130 mg/dL or triglycerides (TG) > 130 mg/dL), high-density lipoprotein cholesterol (HDL-C) < 40 mg/dL; (4) if routinely taking medication for lowering blood glucose, blood pressure, or lipid levels, there should not be significant dosage changes within the past three months; (5) being willing to participate after receiving an explanation from the physician, completing the trial plan, and signing the consent form. The exclusion criteria included: (1) history of diabetic ketoacidosis; (2) medical records indicating the occurrence of cerebrovascular disease, acute myocardial infarction, coronary artery bypass surgery, placement of coronary artery stents, or peripheral vascular disease within the last 6 months; (3) occurrence of acute infectious diseases within the last month and antibiotic use for > 7 days; (4) short-term use of steroids, NSAIDs, immunosuppressive drugs, interferons, immunomodulators, or any changes in the dose of long-term medications within the last month; (5) use of any weight-loss drugs in the last three months (including Orlistat, Lorcaserin, liraglutide); (6) history of any cancer or undergoing cancer treatment in the past 5 years; (7) abnormal liver function (GOT or GPT greater than 3 times the normal upper limit) or liver cirrhosis; (8) impaired kidney function (eGFR < 30 mL/min/1.73 m²); (9) history of alcohol abuse; (10) participation in any other interventional clinical research within the last month; (11) pregnant and breastfeeding women; (12) history of allergy to the investigational product; (13) participants deemed unsuitable for inclusion by the principal investigator.

Study Design and Intervention:

Enrolled participants were randomly divided into probiotics group or placebo group. Seventeen and 19 participants were respectively assigned to the placebo group and the probiotics group. The probiotics we used were in the form of 100mg L. bulgaricus powder packets, each containing 1×10^8 CFU of probiotics (TCI CO., Taipei, Taiwan). Initially (day 1), participants underwent measurements for weight, body fat, and BMI, and fasting blood

[figure not shown]
IRB/REC No. :	CMUH110-REC2-070
Page No. :	5/28

samples were collected. Subsequently, each participant received one package of either probiotic or a placebo sample, along with drinking water on the same day. From that point onward, participants self-administered one package of the sample daily for 12 weeks and the participants' sample consumption and physical conditions were tracked by the research assistants weekly. Throughout the study duration, participants maintained their regular diet and lifestyle. At the endpoint (day 84), weight, body fat, and BMI were measured, and fasting blood samples were collected again. Weight and body fat were measured with Karada Scan 216 (OMRON, Kyoto, Japan). Alanine aminotransferase (ALT), aspartate aminotransferase (AST), blood urea nitrogen (BUN), creatinine (CRE), CHOL, HDL-C, LDL-C, TG, hemoglobin A1c (HbA1c), and Glucose-Ante Cibum (Glu-AC) levels were analyzed and reported by Laboratory Medicine in Chinese Medical University Hospital (Taichung, Taiwan). Data were expressed as the mean \pm standard error of the mean (SEM). Statistical significance between groups were done by student paired t-test or Mann-Whitney test. P-values lower than 0.05 were considered statistically significant.

Data Analysis:

The statistical analysis was conducted using GraphPad's unpaired independent samples t-test, with significance set at $*P < 0.05$.

Flow Diagram of the study:

Group	Placebo		Probiotics	
	Mean	SD	Mean	SD
Age, years	41.38	12.71	41.56	10.92
Gender, male/female	7/6		12/6	
Weight, kg	78.69	15.64	80.77	15.11
Body fat, %	32.08	6.65	30.84	5.26
BMI	29.32	5.40	28.89	3.59
ALT, U/L	26.00	15.37	32.63	18.96
AST, U/L	21.45	10.62	23.36	7.44
BUN, mg/dL	13.10	2.69	13.67	2.94
CRE, mg/dL	0.80	0.14	0.83	0.15
CHOL, mg/dL	182.18	43.04	201.60	40.97
HDL-C, mg/dL	46.82	5.82	48.50	16.26
LDL-C, mg/dL	122.82	42.15	111.01	30.40
TG, mg/dL	139.62	52.18	220.94	173.92
HbA1c, %	5.80	0.83	6.17	1.07
Glu-AC, mg/dL	93.45	16.92	109.06	34.13

Table 1: Analysis of Baseline Values of the Participants

Results

[figure not shown]

Figure 1: Changes in Body Composition

Placebo represents the placebo control group, and Probiotics represents the probiotics experimental group. The changes in body weight (A), body fat (B), and BMI (C) before and after consumption were calculated and expressed as a percentage of the initial values. No significant differences were observed between the two groups.

[figure not shown]

Figure 2: Changes in Blood Sugar Indices

Placebo represents the placebo control group, and Probiotics represents the probiotics experimental group. The changes in fasting blood glucose (GLU-AC) before and after sample consumption (A) and changes in glycated hemoglobin (HbA1c) expressed as a percentage of the initial values (B) were calculated. No significant differences were observed

between the two groups.

[figure not shown]

Figure 3: Changes in Blood Lipids

Placebo represents the placebo control group, and Probiotics represents the probiotics experimental group. The changes in total cholesterol (CHOL) (A), triglycerides (TG) (B), high-density lipoprotein cholesterol (HDL) (C), and low-density lipoprotein cholesterol (LDL-C) (D) before and after sample consumption were calculated. No significant differences were observed between the two groups. In the probiotics group, 65% of participants showed a decrease in TG concentration, while the placebo group had a decrease rate of 18%.

[figure not shown]

Figure 4: Changes in Liver and Kidney Function

Placebo represents the placebo control group, and Probiotics represents the probiotics experimental group. The changes in liver function indicators, aspartate aminotransferase (AST) (A) and alanine aminotransferase (ALT) (B), as well as kidney function indicators, creatinine (CRE) (C) and blood urea nitrogen (BUN) (D), before and after sample consumption were calculated. No significant differences were observed between the two groups.

IRB/REC No. :	CMUH110-REC2-070
Page No. :	10/28

Table 2: Comparative Analysis of Blood Biochemical Indices Before and After the Experiment and Changes Before and After

Variables		Probiotics	Placebo	P-value ^b
		Mean \pm SEM	Mean \pm SEM	
ALT (U/L)	Pre	32.00 \pm 4.495	31.00 \pm 6.454	0.9897
	Post	28.12 \pm 4.853	37.69 \pm 7.946	0.7713
	Change	-3.882 \pm 3.461	6.692 \pm 6.747	0.5075
	P-value ^a	0.2462	0.3799	
AST (U/L)	Pre	24.31 \pm 1.886	22.38 \pm 3.054	0.3909
	Post	22.44 \pm 2.238	25.85 \pm 4.366	0.9053
	Change	-1.875 \pm 1.530	3.462 \pm 2.043	0.34
	P-value ^a	0.0708	0.1367	
BUN (mg/dL)	Pre	13.82 \pm 0.6765	13.17 \pm 0.8242	0.9267
	Post	12.88 \pm 0.8985	12.67 \pm 0.7914	0.9694
	Change	-0.6250 \pm 0.7465	-0.5000 \pm 0.8118	>0.999
	P-value ^a	0.5256	0.6504	
CRE (mg/dL)	Pre	0.8241 \pm 0.03584	0.7962 \pm 0.0443	0.907
	Post	0.8775 \pm 0.04979	0.7915 \pm 0.04273	0.6543
	Change	0.0475 \pm 0.02713	-0.004615 \pm 0.02087	0.34
	P-value ^a	0.0535	0.8262	
CHOL (mg/dL)	Pre	200.7 \pm 10.33	186.9 \pm 11.49	0.67
	Post	204.6 \pm 12.42	186.3 \pm 10.20	0.0719
	Change	3.882 \pm 7.086	-0.6154 \pm 3.852	0.5075
	P-value ^a	0.6526	0.8535	
Glu-AC (mg/dL)	Pre	109.3 \pm 7.834	91.77 \pm 4.590	0.3871
	Post	100.7 \pm 9.383	91.69 \pm 6.466	0.5854
	Change	1.389 \pm 2.332	-0.07692 \pm 2.962	0.7803
	P-value ^a	0.6183	0.6846	
HbA1c (%)	Pre	6.124 \pm 0.2559	5.800 \pm 0.2295	0.8619
	Post	6.407 \pm 0.3149	5.931 \pm 0.3175	0.6367
	Change	0.2067 \pm 0.05893	0.1308 \pm 0.09765	0.4821
	P-value ^a	0.0029	0.2061	
HDL-C (mg/dL)	Pre	48.55 \pm 3.820	46.82 \pm 1.613	0.3643
	Post	47.38 \pm 3.125	46.43 \pm 1.798	0.4656
	Change	-0.0125 \pm 1.362	-0.3923 \pm 1.590	0.9872
	P-value ^a	0.4037	0.7227	
LDL-C (mg/dL)	Pre	113.0 \pm 7.399	122.8 \pm 12.17	0.4531
	Post	119.0 \pm 5.992	112.4 \pm 8.306	0.5874

IRB/REC No. :	CMUH110-REC2-070
Page No. :	11/28

	Change	6.012 ± 4.366	-12.04 ± 6.323	0.0946
	P-valuea	0.4586	0.0923	
TG (mg/dL)	Pre	220.9 ± 42.18	139.6 ± 14.47	0.5469
	Post	199.9 ± 40.46	177.4 ± 36.55	0.907
	Change	-21.00 ± 11.61	37.77 ± 34.12	0.0555
	P-valuea	0.1075	0.1577	

P-valuea **paired t-test (Pre and Post groups)**

P-valueb **unpaired t-test (Probiotics and Placebo groups)**

[figure not shown]

Figure 5: Changes in Lipids Carried by Serum Lipoproteins

Placebo represents the placebo control group, and Probiotics represents the probiotics experimental group. Individual comparisons of changes in lipids carried by serum lipoproteins before and after sample consumption are depicted. The size of the points in the scatter plot ($-\log_{10}$ p values) and the color (log2 fold change denoted as log2FC, with red indicating positive correlation changes and blue indicating negative correlation changes) are used to distinguish between inter-group differences and trends. Serum very low-density lipoprotein (VLDL), low-density lipoprotein (LDL), and high-density lipoprotein (HDL) have the ability to carry cholesterol (Chol), lipids, cholesterol esters (CE), and triglycerides (TG) individually. The experimental data indicate that probiotics upregulate the content of

IRB/REC No. :	CMUH110-REC2-070
Page No. :	13/28

lipids carried by HDL (Chol:Lipid and CE:Lipid). Simultaneously, there is a significant decrease in the total amount of lipids carried by VLDL (L-VLDL, XL-VLDL, XXL-VLDL). Additionally, there is a significant decrease in triglycerides (TG) carried by both VLDL and HDL.

IRB/REC No. :	CMUH110-REC2-070
Page No. :	14/28

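### The primary goal spans weight, lipids, glucose and insulin with no outcome designated primary and a flat 0.05 per test; insulin was not measured, so that part cannot be answered

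*Combined protocol and SAP*

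**What the plan says.** The Background gives an objective and then a goal. The objective is about weight: "the objective of this study was to examine the effectiveness of daily *L. bulgaricus* supplementation in weight management among overweight participants". The next sentence is wider: "The primary goal is to evaluate its impact on lowering body weight and addressing health risk factors related to obesity", and the risk factors are spelled out as "health risk factors related to obesity, including blood lipid levels, sugar regulation, and insulin levels". Nothing is labelled a primary or secondary outcome.

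Study Design and Intervention sets the measurements: "At the endpoint (day 84), weight, body fat, and BMI were measured, and fasting blood samples were collected again". The laboratory list has ten analytes: ALT, AST, BUN, CRE, CHOL, HDL-C, LDL-C, TG, HbA1c and Glu-AC. It ends "hemoglobin A1c (HbA1c), and Glucose-Ante Cibum (Glu-AC) levels were analyzed and reported by Laboratory Medicine". Insulin is not listed there, nor in Table 1, Table 2 or the biomarker list in Table 3.

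The decision rule is "P-values lower than 0.05 were considered statistically significant". Data Analysis repeats the 0.05 level and names "GraphPad's unpaired independent samples t-test, with significance set at". The sentence just before Data Analysis names a paired t-test or a Mann-Whitney test instead. Neither section mentions an adjustment, a hierarchy or the sidedness of the tests.

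**The concern.** Two defects sit in the same sentence of the plan. First, a quantity named in the primary goal has no data behind it. Second, the rest of the goal is a set of co-equal outcomes, each tested at 0.05, so the plan does not say which result decides whether the trial succeeded. A favourable result on any one of them could be presented as meeting the goal, and a null result on weight would have no formal precedence over it.

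**Working it through.** The documents give no sample-size calculation, power or family-wise error rate, so there is no design figure to reproduce beyond the per-test 0.05.

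**1. Insulin.** The goal in the Background includes it. The laboratory list and Tables 1, 2 and 3 do not. These lists are printed whole, with no sign of redaction.

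**2. Size of the family.** Outcomes measured and named in the goal:
- weight: 1
- lipids (CHOL, HDL-C, LDL-C, TG): 4
- sugar regulation (Glu-AC, HbA1c): 2

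The total is 7, or 9 if body fat and BMI are counted with weight.

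**3. Family-wise error, all nulls true, two-sided 0.05 assumed.** If independent, the chance is 1 − 0.95^k:
- k = 7: 1 − 0.95^7 = 0.302
- k = 9: 1 − 0.95^9 = 0.370

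The outcomes are correlated, but the documents give no correlations. Simulating equicorrelated normal statistics (400,000 draws) with assumed values gives:

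| Assumed correlation | 7 outcomes | 9 outcomes |
|---|---|---|
| 0.3 | 27% | 33% |
| 0.5 | 23% | 27% |
| 0.8 | 15% | 17% |

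Bonferroni thresholds for co-equal outcomes would be 0.05/7 = 0.0071 or 0.05/9 = 0.0056.

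**4. LDL-C as an illustration.** Table 2 prints the changes (mean ± SEM) as 6.012 ± 4.366 for probiotics and −12.04 ± 6.323 for placebo, P = 0.0946, labelled unpaired t-test. Table 2 gives no group sizes. Table 1's sex counts give 18 and 13, so 15-18 and 12-13 are assumed here.
- Difference: 6.012 + 12.04 = 18.05 mg/dL, unfavourable to the probiotic.
- Pooled test with 18 and 13: variances 4.366² × 18 = 343.1 and 6.323² × 13 = 519.7; pooled variance (17 × 343.1 + 12 × 519.7)/29 = 416.2; SE = √[416.2 × (1/18 + 1/13)] = 7.43; t = 2.43 on 29 df; P = 0.0215.
- Welch test: SE = √(4.366² + 6.323²) = 7.68; t = 2.35; P about 0.028.
- Over all assumed sizes: pooled 0.022-0.024, Welch 0.028-0.029.
- Bonferroni: over 7, 0.0215 × 7 = 0.15 to 0.029 × 7 = 0.20; over 9, 0.19 to 0.26. It passes neither.

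The printed placebo means differ by 112.4 − 122.8 = −10.4, not −12.04, perhaps because different participants contribute. Using −10.4 with the printed SEM gives P of about 0.035-0.045.

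**5. Metabolomics.** In Tables 4 and 5 the yes/no flag follows the raw P-value, although an adjusted column is printed. Table 5 flags 30 of about 250 features; 250 × 0.05 = 12.5 would be expected by chance. Its largest −log10 adjusted value is 0.805, so the smallest adjusted P is 10^−0.805 = 0.157. For the total lipids in L-, XL- and XXL-VLDL that the Figure 5 legend calls significantly decreased, the raw P-values are 10^−1.334 = 0.046, 0.046 and 10^−1.494 = 0.032. The adjusted value is 10^−0.407 = 0.39 for each. Both tables are pre/post comparisons within one arm, not comparisons between arms.

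**The case against.** The strongest reply is that nothing went wrong in the clinical results. The legends of Figures 1 to 4 report no significant difference between groups for body composition, glucose, lipids, or liver and kidney function. The title and the objective sentence already point to weight, and no conclusion about insulin is drawn. All of this is correct. It limits the practical effect of the flat 0.05 rule on the clinical outcomes, but it does not supply a designated primary outcome or any insulin data.

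Three stronger readings are tempting and are not supported.
- A reader might count all 13 clinical measurements and quote 1 − 0.95^13 = 49%. The goal does not include ALT, AST, BUN or CRE, and the Figure 4 legend presents them as liver and kidney function indicators. The family is 7 or 9.
- A reader might infer that the trial's own rule yields two laboratory effects, LDL-C and AST (AST recomputes to about 0.041-0.049 against a printed 0.34). That holds only under the unpaired t-test and assumed group sizes. The plan also names a Mann-Whitney test, which cannot be recomputed from means and SEMs, and the report declares neither effect. AST is also borderline and outside the goal. The mismatch with the printed P-values is a separate matter of test labelling.
- A reader might infer that naming a primary outcome now would restore 5% error control. The results are already known, so it cannot do so fully.

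**Conclusion.** The concern holds. The insulin part of the primary goal cannot be answered, no outcome is designated primary, and the measured goal outcomes carry a false-positive risk of 30-37% if independent, or about 15-33% under assumed correlations of 0.3-0.8. Every scenario examined is about three or more times the nominal 5%.

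The missing ranking has consequences in two places. Under the test labelled in Table 2, and with the assumed group sizes, the LDL-C change would fall at about 0.02-0.03 against the probiotic, yet would not survive adjustment over the goal outcomes; the plan has no rule for reading such a result. The Figure 5 claims are where an unadjusted 0.05 drives a stated conclusion, and no feature in Table 5 reaches 0.05 after the adjustment printed beside it.

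**What to change.** - Remove insulin from the primary goal, or state that it was not measured.
- Make the between-arm difference in body-weight change from baseline to day 84 the single primary test at two-sided 0.05, adjusted for baseline weight (for example ANCOVA). Raw day-84 weight would be a poor contrast: if its SDs resemble those in Table 1 (15.11 and 15.64 kg), with 18 and 13 participants the SE is about 5.6 kg.
- Apply Holm to the eight remaining efficacy outcomes: body fat, BMI, CHOL, HDL-C, LDL-C, TG, Glu-AC and HbA1c.
- Report ALT, AST, BUN and CRE as safety outcomes with unadjusted estimates and confidence intervals. Report any unfavourable lipid change the same way, so that adjustment does not hide possible harm.
- Label metabolomics exploratory, judge it on the printed adjusted P-values, and withdraw the word *significant* from the Figure 5 legend.
- State that this ranking was set after the data were seen.

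The cost is new wording in the SAP and report, plus re-analysis of data already collected. Secondary outcomes become harder to call significant, and a post hoc ranking cannot fully restore error control.

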Appendix

Figure 5: Extracted Meaningful Components from Metabolomic Analysis Results, Other Results Provided in the Appendix °

Table 3: List of Name Abbreviations and Units

Excel column name	Biomarker name	Unit
Total-C	Total cholesterol	mmol/l
non-HDL-C	Total cholesterol minus HDL-C	mmol/l
Remnant-C	Remnant cholesterol (non-HDL, non-LDL -cholesterol)	mmol/l
VLDL-C	VLDL cholesterol	mmol/l
Clinical LDL-C	Clinical LDL cholesterol	mmol/l
LDL-C	LDL cholesterol	mmol/l
HDL-C	HDL cholesterol	mmol/l
Total-TG	Total triglycerides	mmol/l
VLDL-TG	Triglycerides in VLDL	mmol/l
LDL-TG	Triglycerides in LDL	mmol/l
HDL-TG	Triglycerides in HDL	mmol/l
Total-PL	Total phospholipids in lipoprotein particles	mmol/l
VLDL-PL	Phospholipids in VLDL	mmol/l
LDL-PL	Phospholipids in LDL	mmol/l
HDL-PL	Phospholipids in HDL	mmol/l
Total-CE	Total esterified cholesterol	mmol/l
VLDL-CE	Cholesteryl esters in VLDL	mmol/l
LDL-CE	Cholesteryl esters in LDL	mmol/l
HDL-CE	Cholesteryl esters in HDL	mmol/l
Total-FC	Total free cholesterol	mmol/l
VLDL-FC	Free cholesterol in VLDL	mmol/l
LDL-FC	Free cholesterol in LDL	mmol/l
HDL-FC	Free cholesterol in HDL	mmol/l
Total-L	Total lipids in lipoprotein particles	mmol/l
VLDL-L	Total lipids in VLDL	mmol/l
LDL-L	Total lipids in LDL	mmol/l
HDL-L	Total lipids in HDL	mmol/l
Total-P	Total concentration of lipoprotein particles	mmol/l
VLDL-P	Concentration of VLDL particles	mmol/l
LDL-P	Concentration of LDL particles	mmol/l
HDL-P	Concentration of HDL particles	mmol/l
VLDL size	Average diameter for VLDL particles	nm
LDL size	Average diameter for LDL particles	nm
HDL size	Average diameter for HDL particles	nm
Phosphoglyc	Phosphoglycerides	mmol/l

IRB/REC No. :	CMUH110-REC2-070
Page No. :	15/28

TG/PG	Ratio of triglycerides to phosphoglycerides	ratio
Cholines	Total cholines	mmol/l
Phosphatidylc	Phosphatidylcholines	mmol/l
Sphingomyelins	Sphingomyelins	mmol/l
ApoB	Apolipoprotein B	g/l
ApoA1	Apolipoprotein A1	g/l
ApoB/ApoA1	Ratio of apolipoprotein B to apolipoprotein A1	ratio
Total-FA	Total fatty acids	mmol/l
Unsaturation	Degree of unsaturation	degree
Omega-3	Omega-3 fatty acids	mmol/l
Omega-6	Omega-6 fatty acids	mmol/l
PUFA	Polyunsaturated fatty acids	mmol/l
MUFA	Monounsaturated fatty acids	mmol/l
SFA	Saturated fatty acids	mmol/l
LA	Linoleic acid	mmol/l
DHA	Docosahexaenoic acid	mmol/l
Omega-3 %	Ratio of omega-3 fatty acids to total fatty acids	%
Omega-6 %	Ratio of omega-6 fatty acids to total fatty acids	%

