L-HDL-FC %	Free cholesterol to total lipids ratio in large HDL	%
L-HDL-TG %	Triglycerides to total lipids ratio in large HDL	%
M-HDL-PL %	Phospholipids to total lipids ratio in medium HDL	%
M-HDL-C %	Cholesterol to total lipids ratio in medium HDL	%
M-HDL-CE %	Cholesteryl esters to total lipids ratio in medium HDL	%
M-HDL-FC %	Free cholesterol to total lipids ratio in medium HDL	%
M-HDL-TG %	Triglycerides to total lipids ratio in medium HDL	%
S-HDL-PL %	Phospholipids to total lipids ratio in small HDL	%
S-HDL-C %	Cholesterol to total lipids ratio in small HDL	%
S-HDL-CE %	Cholesteryl esters to total lipids ratio in small HDL	%
S-HDL-FC %	Free cholesterol to total lipids ratio in small HDL	%
S-HDL-TG %	Triglycerides to total lipids ratio in small HDL	%

IRB/REC No. :	CMUH110-REC2-070
Page No. :	20/28

Table 4: Comparative Analysis of Metabolomic Pre-test and Post-test Results for Placebo Group Blood Samples

Differential expression analysis								
Significance(p-value)	Feature	Mean(after)	Mean(before)	Method	FC	Log2(FC)	-Log10(p-value)	-Log10(padj)
yes	Creatinine	64.21	59.285	t-test	0.923	-0.115	2.023	0.103
yes	IDL_CE_pct	51.149	49.621	t-test	0.97	-0.044	2.623	0.527
yes	IDL_C_pct	67.73	66.121	t-test	0.976	-0.035	2.767	0.527
yes	IDL_TG_pct	8.787	10.075	t-test	1.147	0.197	1.332	0.06
yes	L_LDL_CE_pct	53.99	53.463	t-test	0.99	-0.014	1.562	0.06
yes	L_LDL_C_pct	71.967	71.136	t-test	0.988	-0.017	1.59	0.06
yes	L_LDL_TG_pct	5.966	6.83	t-test	1.145	0.195	1.397	0.06
yes	M_LDL_PL_pct	26.658	26.309	t-test	0.987	-0.019	1.452	0.06
no	Acetate	0.017	0.019	t-test	1.092	0.126	0.309	0.06
no	Acetoacetate	0.025	0.019	t-test	0.741	-0.432	0.366	0.06
no	Acetone	0.019	0.021	t-test	1.063	0.089	0.067	0.005
no	Ala	0.337	0.383	t-test	1.137	0.185	1.234	0.06
no	Albumin	41.434	40.602	t-test	0.98	-0.029	0.259	0.06
no	ApoA1	1.416	1.353	t-test	0.955	-0.066	0.477	0.06
no	ApoB	0.878	0.858	t-test	0.977	-0.033	0.24	0.06
no	ApoB_by_ApoA1	0.63	0.642	t-test	1.019	0.027	0.179	0.027
no	bOHbutyrate	0.094	0.103	t-test	1.1	0.137	0.063	0.005
no	Cholines	2.554	2.454	t-test	0.961	-0.058	0.361	0.06
no	Citrate	0.06	0.063	t-test	1.043	0.061	1.126	0.06
no	Clinical_LDL_C	2.787	2.6	t-test	0.933	-0.101	0.605	0.06
no	DHA	0.323	0.291	t-test	0.9	-0.152	0.271	0.06
no	DHA_pct	2.574	2.387	t-test	0.927	-0.109	0.292	0.06
no	Gln	0.487	0.495	t-test	1.016	0.022	0.099	0.005
no	Glucose	4.525	3.994	t-test	0.883	-0.18	0.749	0.06
no	Gly	0.251	0.302	t-test	1.202	0.265	1.129	0.06
no	GlycA	0.857	0.83	t-test	0.968	-0.046	0.294	0.06

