no	XXL_VLDL_P	0	0	t-test	0.992	-0.012	0.01	0.002
no	XXL_VLDL_PL	0.026	0.026	t-test	0.986	-0.021	0.017	0.002
no	XXL_VLDL_PL_pct	14.889	16.636	t-test	1.117	0.16	0.527	0.06
no	XXL_VLDL_TG	0.084	0.074	t-test	0.879	-0.187	0.136	0.01
no	XXL_VLDL_TG_pct	34.697	43.814	t-test	1.263	0.337	0.413	0.06

IRB/REC No. :	CMUH110-REC2-070
Page No. :	25/28

Table 5: Comparative Analysis of Metabolomic Pre-test and Post-test Results for Probiotics Group Blood Samples

Differential expression analysis								
Significance(p-value)	Feature	Mean(after)	Mean(before)	Method	FC	Log2(FC)	-Log10(p-value)	-Log10(padj)
yes	Acetate	0.017	0.019	t-test	1.156	0.209	1.329	0.407
yes	Gly	0.263	0.295	t-test	1.123	0.167	1.447	0.407
yes	HDL_size	9.573	9.508	t-test	0.993	-0.01	1.433	0.407
yes	Lactate	4.175	5.984	t-test	1.433	0.519	1.441	0.407
yes	L_VLDL_CE_pct	14.036	15.354	t-test	1.094	0.129	1.363	0.407
yes	L_VLDL_C_pct	28.119	29.999	t-test	1.067	0.093	1.505	0.407
yes	L_VLDL_FC_pct	14.083	14.645	t-test	1.04	0.056	1.643	0.421
yes	L_VLDL_L	0.563	0.48	t-test	0.853	-0.229	1.334	0.407
yes	L_VLDL_TG	0.288	0.233	t-test	0.81	-0.304	2.037	0.533
yes	L_VLDL_TG_pct	51.128	49.056	t-test	0.959	-0.06	1.429	0.407
yes	M_HDL_CE_pct	37.7	39.269	t-test	1.042	0.059	2.902	0.805
yes	M_HDL_C_pct	46.11	47.515	t-test	1.03	0.043	3.121	0.805
yes	M_HDL_PL_pct	47.018	46.34	t-test	0.986	-0.021	1.977	0.533
yes	M_HDL_TG_pct	6.873	6.145	t-test	0.894	-0.161	1.715	0.463
yes	M_VLDL_PL_pct	21.414	22.043	t-test	1.029	0.042	1.319	0.407
yes	S_HDL_CE_pct	27.533	28.901	t-test	1.05	0.07	1.987	0.533
yes	S_HDL_C_pct	37.973	39.337	t-test	1.036	0.051	2.162	0.533
yes	S_HDL_PL_pct	55.964	55.036	t-test	0.983	-0.024	1.839	0.52
yes	S_HDL_TG_pct	6.063	5.628	t-test	0.928	-0.107	1.571	0.407
yes	S_LDL_C_pct	62.862	63.718	t-test	1.014	0.019	2.566	0.645
yes	TG_by_PG	0.778	0.696	t-test	0.895	-0.161	1.792	0.508
yes	VLDL_size	39.666	39.173	t-test	0.988	-0.018	2.006	0.533
yes	VLDL_TG	1.623	1.384	t-test	0.853	-0.229	1.355	0.407
yes	XL_HDL_CE_pct	36.249	38.447	t-test	1.061	0.085	1.922	0.524
yes	XL_HDL_C_pct	52.182	56.422	t-test	1.081	0.113	1.345	0.407
yes	XL_VLDL_L	0.381	0.323	t-test	0.847	-0.239	1.334	0.407
yes	XL_VLDL_TG	0.221	0.181	t-test	0.818	-0.291	1.843	0.52
yes	XXL_VLDL_L	0.467	0.375	t-test	0.804	-0.315	1.494	0.407
yes	XXL_VLDL_P	0	0	t-test	0.817	-0.292	1.395	0.407
yes	XXL_VLDL_TG	0.267	0.202	t-test	0.756	-0.403	2.073	0.533
no	Acetoacetate	0.026	0.017	t-test	0.651	-0.619	0.697	0.243
no	Acetone	0.016	0.02	t-test	1.238	0.308	0.6	0.219

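### Metabolite features are flagged on unadjusted p-values, and several are called significant in the Figure 5 text, although no adjusted p-value in Tables 4 and 5 is below 0.05 in either arm

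*Combined protocol and SAP*

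**What the plan says.** Methods and Design gives the significance rule twice. At the end of Study Design and Intervention it reads "P-values lower than 0.05 were considered statistically significant". Under Data Analysis it reads "The statistical analysis was conducted using GraphPad's unpaired independent samples t-test, with significance set at" 0.05. Neither place mentions multiplicity or the metabolomic panel.

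Appendix Tables 4 (placebo) and 5 (probiotics) compare each feature before and after within one arm. Each has a yes/no column whose header begins "Significance(p-value", and a last column giving -log10 of an adjusted p-value. The adjustment method is not named. The strongest row in Table 4 is "IDL_C_pct 67.73 66.121 t-test 0.976 -0.035 2.767 0.527", where the last two figures are -log10(p) and -log10(padj). The weakest flagged row there is "IDL_TG_pct 8.787 10.075 t-test 1.147 0.197 1.332 0.06". The strongest row in Table 5 is "M_HDL_C_pct 46.11 47.515 t-test 1.03 0.043 3.121 0.805".

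The Figure 5 legend in Results reports a significant fall in total lipids in L-, XL- and XXL-VLDL, and adds that "there is a significant decrease in triglycerides (TG) carried by both VLDL and HDL". It describes the HDL cholesterol-to-lipid ratios as upregulated, without using the word significant. It does not mention the adjusted p-values. The Appendix note on the figure describes its content as "Extracted Meaningful Components from Metabolomic Analysis Results" and points to the Appendix for the rest.

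**The concern.** With some 250 tests in each arm, a 0.05 cut on raw p-values yields flagged features even if nothing changed. The analysts evidently computed an adjustment, yet the flag and the legend text follow the unadjusted column. This matters because Figures 1 to 4 report no significant between-group difference, and no between-group change in Table 2 has p below 0.05 (the smallest is 0.0555, for TG). The Figure 5 legend therefore carries the report's only favourable significance claims. If the adjusted column printed beside them contradicts them, a reader who relies on the legend is misled.

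**Working it through.** **Inputs.** -log10(p) and -log10(padj) from Tables 4 and 5; the feature list from Table 3. The printed p-values are taken as given.

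**Number of tests.** Table 3 lists 14 lipoprotein subclasses with 12 measures each, plus 82 other biomarkers: 14 × 12 + 82 = 250 per arm.

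**Reproducing the adjusted column.** Benjamini-Hochberg gives -log10(padj) = -log10(p) - log10(m/rank), made monotone so that a row takes the best value at its own or any later rank. With m = 250:

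| Table | Row that sets the value | Rank | Calculation | Result | Printed |
|---|---|---|---|---|---|
| 5 | M_HDL_CE_pct | 2 | 2.902 - log10(250/2) | 0.805 | 0.805 |
| 5 | S_LDL_C_pct | 3 | 2.566 - log10(250/3) | 0.645 | 0.645 |
| 5 | M_HDL_PL_pct | 9 | 1.977 - log10(250/9) | 0.533 | 0.533 |
| 5 | XL_VLDL_CE_pct | 46 | 1.142 - log10(250/46) | 0.407 | 0.407 |
| 4 | IDL_CE_pct | 2 | 2.623 - log10(250/2) | 0.526 | 0.527 |

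Rank 46 in Table 5 is the 30 flagged rows plus the 16 strongest unflagged ones, and it explains why so many rows share 0.407. The Table 4 difference is within rounding, and m = 249 fits that table equally well. The column thus behaves as Benjamini-Hochberg over about 250 tests.

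**Comparison with the threshold.** An adjusted p of 0.05 needs -log10(padj) = 1.301.

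| | Placebo | Probiotics |
|---|---|---|
| Flagged on raw p | 8 | 30 |
| Raw p of flagged rows | 0.0017 to 0.047 | 0.00076 to 0.048 |
| Largest -log10(padj) | 0.527 | 0.805 |
| Smallest padj | 10^-0.527 = 0.297 | 10^-0.805 = 0.157 |
| Largest padj among flagged rows | 10^-0.06 = 0.87 | 10^-0.407 = 0.39 |
| Passing at 5%, 10% or 15% | 0 | 0 |
| Passing at 20% | 0 | 2 (M_HDL_C_pct, M_HDL_CE_pct) |

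Bonferroni gives the same answer at 0.05: 250 × 0.0017 = 0.43 in placebo and 250 × 0.00076 = 0.19 in probiotics.

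**Claims in the Figure 5 legend, read against Table 5.**
- L-, XL- and XXL-VLDL total lipids: -log10(padj) 0.407 each, so padj = 0.39.
- VLDL triglycerides: L and XXL 0.533 (padj 0.29), XL 0.520 (0.30), total VLDL_TG 0.407 (0.39).
- HDL triglycerides as an amount: HDL_TG has -log10(p) = 0.361, so raw p = 0.44. M_HDL_TG (0.427) and S_HDL_TG (0.238) are also unflagged. Only the percentages M_HDL_TG_pct (padj 10^-0.463 = 0.34) and S_HDL_TG_pct (0.39) are flagged.

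**Chance expectation.** If every null held, 250 × 0.05 = 12.5 features per arm would be flagged on average. Placebo has 8 and probiotics 30.

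**Direction.** L_VLDL_L in Table 5 is printed as 0.563 after and 0.48 before, with FC 0.853 = 0.48/0.563. As labelled it rises, while the legend reports a decrease. Table 2 does not settle which label is right. In the probiotics arm its TG falls by 21.00 mg/dL, whereas Total_TG in Table 5 rises as labelled (1.976 to 2.227). Creatinine, however, rises both in Table 2 (by 0.0475 mg/dL) and as labelled in Table 5 (68.671 to 72.354).

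**The case against.** The strongest reply is that the panel is supplementary and openly reported. The stated goals are weight and routine risk factors, for which the report claims no between-group significance. Tables 4 and 5 print the whole panel with raw and adjusted values, and the flag column says it rests on the p-value. All of that stands. A reader might infer that unfavourable features or the adjusted results were withheld, but the Appendix shows every row. The fault lies in the flag and the wording.

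A second reply is that 30 flagged features in probiotics is well above 12.5. The mean is valid under correlation, but the features are nested totals and ratios that move together, so counts vary widely. The excess cannot be read as evidence of effect, nor can placebo's 8 as evidence of none. The legend makes claims about individual features, and no individual feature passes.

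A third reply is that 5% is strict for an exploratory, correlated panel. A looser rate could be defended if declared, but the legend neither declares one nor calls the panel exploratory. At 20% only two HDL cholesterol ratios would pass, and none of the VLDL or triglyceride claims.

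Finally, the legend speaks of differences between groups and the figure itself is not available, so its p-values might not be those of Table 5. The named VLDL features match the Table 5 flags, but the link is an inference. No between-arm metabolite test is tabulated that could support the legend instead.

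**Conclusion.** The point stands on the documents' own figures. On the printed adjusted p-values the count of significant features falls from 8 to 0 in placebo and from 30 to 0 in probiotics. The VLDL claims have adjusted p of 0.29 to 0.39, and the HDL triglyceride claim as an amount fails before any adjustment, so multiplicity is not the reason there.

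The conclusion that nothing passes rests only on the printed column. That the method is Benjamini-Hochberg with m of about 250 is inferred from the numerical match.

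Two stronger readings are not supported. A reader might infer that the panel shows the probiotic has no metabolic effect; failing an adjusted test in a small trial does not show that. A reader might also infer that a passing adjusted value in Table 5 would demonstrate a treatment effect; it would not, because these are before/after tests within one arm. The reported absence of between-group differences in Figures 1 to 4 is untouched by this point.

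**What to change.** Text and table edits, needing no new data or analysis:
- Base the significance flag in Tables 4 and 5 on adjusted p < 0.05, and name the adjustment method and the number of tests in Data Analysis.
- State that no feature passes in either arm.
- Remove the word significant from the Figure 5 text, give the adjusted p-values there, and limit the HDL triglyceride statement to the two percentages concerned.
- Label the panel exploratory and within-arm. The full feature list is already in the Appendix, so no further table is needed.
- Reconcile the before and after headers, the FC definition and the stated direction against the source data.

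If any treatment-effect claim is kept, base it on between-arm comparisons of change for all features, with multiplicity adjustment across the panel. This is more than a text edit, but it is a modest re-analysis of data already collected. The other cost is the loss of the report's only favourable significance statement.
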